# 13.4. Efficacy Analyses

### 13.4.1 Analysis of Primary Endpoint

The data cut-off for the Week 12 analysis at the end of the study will occur after all treated subjects have completed at least the Week 12 assessment; completed the final study visit; or terminated early from the study. The DCR at Week 12 is defined as the percentage of subjects with a response of CR, PR or SD at the Week 12 assessment, as per modified RECIST [Nowak, 2005] for thoracic disease or RECIST 1.1 elsewhere.

Subjects with non-evaluable or missing response will be treated as not having disease controlled; i.e., they will be included in the denominator when calculating the DCR. As a specific example, subjects with disease progression or death prior to the Week 12 assessment will be included in the denominator. In addition to the DCR at Week 12, an exact 90% CI for this rate will be provided.

## 13.4.2 Analysis of Secondary Efficacy Endpoints

The ORR and an exact 90% CI will be provided.

Data cut-off for Week 12 is defined in Section 13.4.1. The data cut-off for the Week 24 analysis will occur after all subjects have completed at least the Week 24 assessment, completed the final study visit, or terminated early from the study, whichever is sooner.

**Progression-Free Survival (PFS)** is defined as the interval of time between the date of the first dose of study drug and the earliest date of disease progression or death due to any cause.

- For subjects who progressed or died after an extended period without adequate assessment, the time of PFS will be censored at their date of last adequate assessment prior to progression or death even if subsequent information is available regarding progression or death. An adequate assessment is defined as an assessment where the investigator determined response is CR, PR, or SD. The date of response at that assessment will be used for censoring. Specific rules for identifying extended loss to follow-up or extended time without an adequate assessment are provided in the SAP.
- For subjects who receive subsequent anti-cancer therapy prior to the date of documented progression or death, the time of PFS will be censored at the last adequate assessment (i.e., last assessment of CR, PR or SD) prior to the initiation of that anti-cancer therapy.
- For other subjects who do not progress or die, the time of PFS will be censored at the date of the last adequate tumor assessment.

**Overall Survival (OS)** is defined as the interval of time between the date of the first dose of study drug and the date of death due to any cause. For subjects who do not die, the time of death will be censored at the date of last contact. Death due to any cause will be included.

Within each part and overall, PFS and OS will be calculated using the Kaplan-Meier method. PFS and OS at 12 weeks, 24 weeks, and overall along with the associated 90% CIs will be provided. If there are a sufficient number of PFS events (i.e., progressions or deaths), median PFS, first and third quartiles and 90% CI, will be estimated using the Brookmeyer-Crowley method [Brookmeyer, 1982]. If there are a sufficient number of deaths, median OS, first and

third quartiles and 90% CI, will be estimated using the Brookmeyer-Crowley method. Figures and listings of PFS and OS will also be provided.

**Response Duration,** for the subset of subjects with confirmed CR or PR response, is defined as the interval of time from the first documented evidence of CR or PR until the first documented disease progression or death due to any cause, using disease-appropriate standardized response criteria.

The DOR will be calculated for each subject with a confirmed CR or PR. If sample size permits, the median DOR will be calculated from the Kaplan-Meier estimates. First and third quartiles will also be calculated along with associated 90% CIs if there are a sufficient number of responders who subsequently progress or die due to any cause. A listing of DOR will be provided.

# 13.5. Safety Analyses

## 13.5.1 Extent of Exposure

The data on exposure to tazemetostat will be listed. Details pertaining to dose interruption or dose modification will also be listed. Duration of exposure and percentage of treatment compliance will be summarized.

### 13.5.2 Adverse Events

The data listings of AEs in the CSR will contain the verbatim description, PT and SOC MedDRA-level terms.

Treatment-emergent AEs (TEAEs) are defined by applying treatment-emergent signs and symptoms (TESS) philosophy. AEs will be regarded as TEAEs if one of the following conditions is met:

- Emerge after the time of first dose administration, having been absent prior to the first dose.
- Re-emerge, having been present but stopped prior to the time of first dose administration.
- Worsen in severity after the time of first dose administration relative to the pre-treatment state, when the AE is continuous.

An AE with partial or completely missing start date and/or time will always be assumed as TEAE, unless it can be determined to be "prior to administration" from the incomplete start date/time or resolution date/time (e.g., month, year is before first administration date, or resolution date is before first administration date).

Only TEAEs will be summarized. Summaries of TEAEs will consist of the number and percentage of subjects reporting the AE by SOC and by PT. TEAEs which occur more than once for a subject will be counted only once in the subject frequencies. TEAEs with different CTCAE grades for a subject will be counted at the worst (highest) grade for the same SOC (likewise for PT). TEAEs with different drug relationship for a subject will be counted at strongest relationship for the same SOC (likewise for PT). TEAEs with missing relationship to study treatment will be counted as "related". TEAEs with missing CTCAE grade will be counted as Grade 3 ("severe").

Summaries of TEAEs by study part and overall will be produced to present the number and percentage of subjects with:

- Any TEAE
- Any treatment-related TEAE
- Any TEAE with CTCAE Grade 3 or higher
- Any TEAE leading to study treatment discontinuation
- Any Serious TEAEs
- Any TEAE of special interest

Listings will be provided for the following:

- AEs
- TEAEs leading to study treatment discontinuation
- Serious TEAEs
- Fatal TEAEs
- TEAEs of special interest

### 13.5.3 Clinical Laboratory Evaluation

All clinical laboratory parameters will be standardized according to the International System of Units (SI) prior to summarization. Separate listings and summary tables (by study part and overall) will be produced for each laboratory test group (complete blood counts, serum chemistries [liver, renal and metabolism] and coagulation profile).

Low, normal, and high (LNH) classifications will be applied to determine whether the laboratory test value was below (L), within (N), or above (H) its reference range. Shifts from baseline in LNH classification and CTCAE grades for each parameter will be summarized by part and overall. The summary will include the worst case shift from baseline during the post-baseline

period, which will include both planned (scheduled) and unscheduled visits after the first dose of study drug. Subjects with laboratory data outside the normal range will be flagged as "L" (Low) or "H" (High) in the data listing.

### 13.5.4 Other Safety Measures

The results of scheduled assessments of physical examination, vital signs, ECG, and ECOG performance status will be summarized by study part and overall. Summaries will include data from scheduled visits. Shifts from baseline will be summarized where appropriate. All data will be listed.

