- e. **ECG:** 12-lead ECG reading must be performed at screening, at Cycle 1 Days 1 and 15, approximately 1 hour after administration of tazemetostat. A single ECG will be recorded unless there is an abnormality, such as prolonged QTc(F) ≥ 480 msec, new arrhythmia, or other clinically significant finding. If an abnormality is observed, the ECG is to be performed in triplicate at least 2 minutes apart. Additional ECG readings will be performed prior to tazemetostat administration on Day 1 of each subsequent cycle. On days when an ECG reading and a PK blood sample collection are scheduled at the same time (Cycle 1 Days 1 and 15 and Day 1 of Cycles 2 through 4), the ECG reading should be performed immediately prior to collection of the PK blood sample, if possible.
- f. **Pregnancy Test:** A serum or urine pregnancy test must be performed at screening and within 21 days of the first dose of study treatment for all females who are of childbearing potential. A separate assessment is required if a negative screening pregnancy test was obtained more than 72 hours before the first dose of study treatment. Subsequent pregnancy tests should be performed on the first day of every cycle of study treatment and may be either urine or serum.

- g. Laboratory Tests: Clinical laboratory tests will be performed at local laboratories according to the laboratory's normal procedures. See Section 8.3.2 for a complete listing of laboratory tests to be performed.
- h. Coagulation Profile: Coagulations tests include prothrombin time (PT) and partial thromboplastin time (PTT).
- i. **PGx:** A single 6-mL blood sample will be collected at screening.
- j. **Circulating DNA:** 20-mL circulating tumor DNA blood samples to be obtained at screening and at time of each tumor assessment including at time of disease progression.
- k. **PK Part 1:** The 12 subjects in Part 1 will have 2-mL blood samples for PK analysis collected at the following time points: Cycle 1 Day 1: pre-dose, 0.5, 1, 2, 4, 6, 8, 10, 12 and 24 hours post-dose; Cycle 1 Day 15: pre-dose, 0.5, 1, 2, 4, 6, 8, 10, and 12 post-dose.

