- q. **Post-Treatment/Early Termination:** A Post-Treatment/Early Termination visit will be conducted within 30 days (±3 days) after the last dose of tazemetostat or prior to the start of a new treatment or therapy at the end of study or if the subject's participation is terminated early. The post-treatment/early termination assessments will be required and, in the event of a continuing AE, the subject will be asked to return for follow-up until the AE has resolved or is deemed to be continuing indefinitely.
- r. **Follow-Up:** Survival follow-up will be conducted approximately every 12 weeks on all subjects, unless they withdraw consent. Information on all anticancer therapies will be collected (the sponsor may choose to stop the collection of therapies after the first anti-cancer treatment following tazemetostat). This may be done by telephone contact.

Table 2: Timing Allowance Windows for Vital Sign Measurements, Pharmacokinetic Sampling, and ECG Measurements

Vital Signs	
Timepoint	Tolerance Window
0 hour	-60 min to 0 hour

Pharmacokinetic Sampling	
Timepoint	Tolerance Window
0 hour	-120 min to 0 hour
>0 hour – 3 hour	-5 minutes/+5 minutes
4 hour – 8 hour	-15 minutes/+15 minutes
10 hour – 12 hour	-30 min/+30 min
24 hour	-60 minutes/+60 minutes

ECG	
Timepoint	Tolerance Window
0 hour	-60 min to 0 hour
>0 hour – 1 hour	-10 minutes/+10 minutes

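### ECG and vital-sign summaries use scheduled visits only, so an off-schedule extreme that is not recorded as an adverse event reaches no summary table (minor)

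*Combined protocol and SAP*

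**What the plan says.** Section 13.5.4 covers four assessments in one sentence: "The results of scheduled assessments of physical examination, vital signs, ECG, and ECOG performance status will be summarized by study part and overall". It then adds "Summaries will include data from scheduled visits" and "Shifts from baseline will be summarized where appropriate". All data are to be listed. The section describes no worst-value table and no QTcF categories.

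Section 13.5.3 treats laboratory data differently. Its summary takes each subject's worst shift over the post-baseline period, "which will include both planned (scheduled) and unscheduled visits after the first dose of study drug".

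ECG timing is set in footnote e of Table 1: "12-lead ECG reading must be performed at screening, at Cycle 1 Days 1 and 15, approximately 1 hour after administration of tazemetostat". For later cycles, "Additional ECG readings will be performed prior to tazemetostat administration on Day 1 of each subsequent cycle". The same footnote and Section 8.3.4 treat a QTcF of 480 msec or more as an abnormality that triggers a triplicate recording. For vital signs, the only timing window in Table 2 is at or before dosing (minus "60 min to 0 hour").

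Section 11.4 requires ECG and vital-sign findings to be recorded as adverse events when the investigator considers them clinically significant, or when they lead to an intervention. Section 13.5.2 tabulates treatment-emergent adverse events with no limit to scheduled visits.

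**The concern.** An ECG or a vital-sign measurement taken between scheduled visits is usually taken for a reason, so extreme values may be more common there than at routine visits. Two adjacent sections of the same plan treat such values in opposite ways, and no reason is given. If the ECG and vital-sign tables are built as 13.5.4 describes, a reader of those tables could not tell that a more extreme value had been recorded at another time. That reader would have to search the listings.

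The baseline raises a smaller, related question. Shifts from baseline are planned, but the plan does not define the ECG baseline, and the scheduled Cycle 1 Day 1 ECG falls about 1 hour after the first dose. A programmer needs to be told which reading to use.

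**Working it through.** The plan states no figure on this point, so there is none to reproduce. The check consists of reading the sections together, followed by one illustration of size.

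**1. Scope of the restriction.** The sentence on scheduled visits does not contain the word *only*. However, it follows a sentence that makes scheduled assessments the thing summarized, and it stands beside a laboratory section that names unscheduled visits expressly. The plain reading is that unscheduled ECGs and vital signs are outside the summaries, shifts included.

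**2. Where a post-dose extreme ends up.**

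| Case | ECG or vital-sign summary (13.5.4) | Adverse-event tables (11.4, 13.5.2) | Listing |
|---|---|---|---|
| (a) Seen at a scheduled assessment | Yes | If significant or acted upon | Yes |
| (b) Seen off schedule, significant or acted upon | No | Yes | Yes |
| (c) Seen off schedule, neither | No | No | Yes |

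Only case (c) is absent from every summary table. In case (b) the event is counted, but the QTcF value behind it is not in the ECG summary.

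**3. Triplicates.** These follow an abnormal reading. If that reading was scheduled, the abnormality is already in scheduled data (case a). The plan does not say whether the triggering reading, one of the three repeats, or an average represents that visit.

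**4. The 480 msec threshold.** Inclusion criterion 12 admits QTcF up to and including 480 msec, and the abnormality threshold is 480 msec or more. The two overlap at exactly 480 msec. A post-baseline count at or above 480 msec is therefore interpretable only beside the baseline category.

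**5. ECG baseline.** A screening ECG is mandatory, so every subject should have a pre-dose reading. Nothing names the Cycle 1 Day 1 ECG as baseline, and nothing expressly rules it out. By analogy, the laboratory section's post-baseline period, which begins after the first dose, would make that ECG post-baseline. The choice matters because Section 2.2.2 gives Tmax as 1-2 hours and a Day 15 to Day 1 AUC ratio of 0.58 at 800 mg BID. Day 1 AUC is thus about 1/0.58 = 1.72 times Day 15 AUC. A reading 1 hour after the first dose would be near a high exposure, and using it as baseline could hide a drug effect in later shifts. Vital signs are timed pre-dose, so this question concerns ECG alone.

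**6. Illustration of size.** Let *p* be the share of subjects in case (c). The documents give no value, so the range below is assumed. Maximum enrolment is 12 + 55 = 67. The expected number missing from every table is 67*p*, and the chance of at least one is 1 - (1 - *p*)^67.

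| Assumed *p* | Expected number | Chance of at least one |
|---|---|---|
| 0.5% | 0.3 | 29% |
| 1% | 0.7 | 49% |
| 2% | 1.3 | 74% |
| 5% | 3.4 | 97% |

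One subject is 1/67 = 1.5% of the maximum enrolment.

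**The case against.** The strongest reply is that nothing important is lost. Clinically significant or acted-upon findings become adverse events and are tabulated without regard to visit schedule, and everything is listed. The named safety endpoints in both parts are adverse events and laboratory tests; ECG and vital signs are not among them. The laboratory data, which are an endpoint, already get the worst-case rule. The extra ECGs that the protocol itself describes are triplicates, and those triggered by a scheduled reading concern an abnormality already in the summary. All of this stands. It confines the point to case (c) and lowers its severity. It does not explain why shifts should ignore part of the data for two measures and not for a third.

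Three stronger readings are tempting, and the documents do not support them.

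- *A reader might infer that the plan uses a drug-exposed ECG baseline.* It does not say so. A pre-dose screening ECG is required, the neighbouring laboratory wording points to a pre-dose baseline, and Section 13.3.3 defers full detail to a SAP whose text is not among the documents supplied. This is a gap in definition, not a stated choice.
- *A reader might infer that the trial's safety endpoint is biased toward no effect.* ECG and vital signs are not the named endpoints, and no direction or amount of bias can be shown without a rate of off-schedule extremes.
- *A reader might size the fault from the pre-dose timing of later ECGs, or from 0/67 reported in place of 1/67.* With Tmax of 1-2 hours, half-life of 3-5 hours and doses assumed 12 hours apart, 2^(-11/3) = 8% to 2^(-10/5) = 25% of peak concentration remains at the next dose. That describes the ECG schedule, not the summary rule. Section 13.5.4 plans no outlier count, so no 0/67 would be reported.

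**Conclusion.** The point holds as a minor one. Section 13.5.4 restricts ECG and vital-sign summaries and shifts to scheduled visits, in contrast to 13.5.3. Off-schedule extremes that do not become adverse events would be found only in listings. How many subjects this affects cannot be known from the documents; the table of assumed rates shows a range from well under one subject to about three of 67. The conclusion rests on the plain reading of 13.5.4 and on no separate SAP text overriding it. The undefined ECG baseline is a clarification to make at the same time, not a second fault. Only descriptive safety reporting is affected; efficacy, alpha, power and sample size are not.

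**What to change.** In Section 13.5.4, or in the SAP, make these changes:

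1. Keep visit-wise summaries on scheduled visits.
2. Base shift and worst-value summaries for ECG (QTcF) and vital signs on the worst post-baseline value over all scheduled and unscheduled assessments, as 13.5.3 does for laboratory data.
3. Tabulate subjects with a post-baseline QTcF at or above 480 msec against their baseline category, since a subject may enter at exactly 480 msec.
4. State which value represents a triplicate set. The rule should not drop the reading that triggered it; a plain average of the repeats alone would do so.
5. State that ECG baseline is the last pre-dose ECG, normally the screening one, because the scheduled Cycle 1 Day 1 ECG is post-dose.

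The cost is a few sentences and one extra descriptive table. No new data are needed: all ECG and vital-sign data are already to be listed, and Section 8.3.4 already sends central ECG readings to the clinical database.

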### 13.6. Pharmacokinetic Analyses

Plasma concentrations of tazemetostat and its metabolite EPZ-6930 will be determined by a validated bioanalytical method. Concentrations of tazemetostat and its metabolite will be listed by study part and nominal time. Standard summary statistics will be calculated (i.e., mean, SD, median, minimum and maximum).

All PK parameters will be calculated using actual times. Population estimates of CL/F, Vd/F, and Ka for tazemetostat will be calculated with a non-linear mixed-effects model using NONMEM 7 software. The effect of subject characteristics such as age, weight, body surface area, and gender on the PK parameters may be investigated. The PK data from this study may be combined with data from other studies to determine the final population PK model. The final population PK model will be described in a separate report.

## 13.7. Exploratory Analysis

As data warrant, exploratory analysis may be performed on each exploratory endpoint listed below. In addition, exploratory analyses may be performed to examine the relationship between exposure to tazemetostat and clinical and safety endpoints (including tumor size or change in tumor size from baseline). The results of these exploratory analyses may be reported separately from the CSR.

- Tumor target gene expression and phenotypic markers including those for differentiation, apoptosis, inflammation and cell proliferation, and their correlation with activity
- Somatic mutation analysis of tumor tissue and blood
- Germline analysis for BAP1 variants

# 14. INDEPENDENT DATA MONITORING COMMITTEE (IDMC)

An IDMC will be utilized in this study to ensure external objective medical and/or statistical review of:

- Safety data at each predetermined (or ad hoc, if needed) and make recommendations to the sponsor to continue, modify or terminate any of the parts or the study
- Efficacy data at the end of Stage 1 in Part 2 to determine if futility has been reached or the study should proceed to subsequent stage

A recommendation of study hold, dose de-escalation, or study termination would be made in the event of the discovery of an unexpected, serious, or unacceptable risk to the subjects in the study.

The schedule of any planned interim analysis and the analysis plan for IDMC review is described in a separate charter.

### 15. STUDY CONDUCT CONSIDERATIONS

# 15.1. Posting of Information on Publicly Available Clinical Trial Registers

Study information from this protocol will be posted on publicly available clinical trial registers before subject enrollment begins.

### 15.2. Regulatory and Ethical Considerations

The procedures set out in this study protocol, pertaining to the conduct, evaluation, and documentation of this study, are designed to ensure that the sponsor and investigators abide by GCP as described in the International Conference on Harmonization (ICH) Tripartite Guideline E6 (R1): GCP: Consolidated Guideline, and for US Investigators, 21 CFR Parts 50, 54, 56, and 312. Compliance with these regulations also constitutes compliance with the ethical principles described in the current revision of the Declaration of Helsinki. The study will also be carried out in keeping with local legal and regulatory requirements.

It is the investigator's responsibility to ensure that adequate time and appropriate resources are available at the study site prior to commitment to participate in this study. The investigator should also be able to estimate or demonstrate a potential for recruiting the required number of suitable subjects within the agreed recruitment period.

The investigator will maintain a list of appropriately qualified persons to whom the investigator has delegated significant study-related tasks. An up-to-date copy of the curriculum vitae for the investigator, sub-investigator(s) and essential study staff will be provided to the sponsor or its designee before starting the study.

If the subject has a primary physician the investigator should, with the subject's or his/her legal representative's consent, inform them of the subject's participation in the study.

